The objective of this study is to investigate blood product use, bleeding events, hospital length of stay, and health care costs in hospitalized patients with cirrhosis and coagulopathy undergoing endoscopy or neurosurgical procedures utilizing ROTEM compared to conventional therapy. Data will be extracted from charts in the electronic medical record (IHIS). Data from charts will be used to construct a secure database of information on risk factors and pre-procedure testing (see Appendix 1). This database will allow analysis of clinical outcomes in patients with cirrhosis undergoing an endoscopic or surgical procedure.

In this prospective study, patients will be randomized into one of two groups:

-Study Group: those who receive blood product transfusions based on ROTEM-guided protocol (Appendix 2). -Control Group: those who receive blood product transfusions based on conventional, laboratory-guided parameters (Appendix 3).

The randomization list will be computer-generated using a balanced allocation ratio of 1:1. The endoscopist or surgeon performing the procedure will be blinded to the patient's group.

B. Hypothesis

The ROTEM- guided transfusion protocol will significantly decrease blood product usage without any increase in procedural bleeding complications versus the conventional, laboratory-based transfusion protocol in patients with cirrhosis undergoing endoscopy and neurosurgical procedures.

C. Objectives

Primary Objective

To compare the total amount of pre-procedure blood products transfused between the ROTEM-guided transfusion protocol and conventional, laboratory-based transfusion protocol in patients undergoing endoscopy and neurosurgical procedures. Endoscopy procedures include esophagogastroduodenoscopy, colonoscopy, flexible sigmoidoscopy, endoscopic retrograde cholangiopancreatography, and endoscopic ultrasound. Neurosurgical procedures may include bedside procedures (e.g. placement of an external ventricular drain or placement of an intracranial pressure monitor), or any neurosurgical cranial or spinal procedure that occurs in the operating room

WEXNER MEDICAL CENTER

during the patient's admission (e.g. craniotomy for evacuation of hematoma or a spinal fusion procedure to address spinal instability).

Secondary Objectives

- 1. Compare the rate of bleeding events between ROTEM vs. conventional therapy:

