 - Clinically significant peri-procedure blood loss as documented by the endoscopist or surgeon performing the procedure
 - Major bleeding during the 24 hours post-procedure, defined as a decrease in hemoglobin of ≥ 2 g/dL or requiring a transfusion of ≥ 2 units of packed red blood cells.
- 2. Compare length of stay between ROTEM vs. conventional therapy
- 3. Compare hospitalization costs between ROTEM vs. conventional therapy

D. Sample

202 patients with cirrhosis and coagulopathy who are undergoing an endoscopic or neurosurgical procedure, at The Ohio State University Wexner Medical Center will be enrolled into the study using the inclusion/exclusion criteria below. Coagulopathy will be corrected by ROTEM-guided transfusion protocol (Appendix 2) or conventional, laboratory-based transfusion protocol (Appendix 3) prior to procedure using a 1:1 randomization.

For the primary aim, a total sample size of 202 patients (101 patients in both the non-ROTEM and ROTEM groups) is required to achieve 80% power for a two-sample t-test to detect a 100% increase in the geometric mean of the non-ROTEM group over the ROTEM group. Significance is defined as a two-sided p-value of less than 0.05. This calculation was based off of pilot data which contained 8 ROTEM and 8 non-ROTEM patients. The secondary aim, demonstrating that the proportion of bleeding events in ROTEM patients is equivalent to or less than the proportion in non-ROTEM patients requires a sample size of 446 patients per group. This calculation assumed that both ROTEM and non-ROTEM patients experience a bleeding event 10% of the time. It was further assumed that the proportion of bleeding events in the ROTEM group will be considered to be equivalent to that of the non-ROTEM group if the proportion is no more than 5% larger. The secondary aim is exploratory in nature for the purposes of this protocol as the sample size for the current study is only 202 patients.

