The requested data fields include demographic data, clinicopathologic data, and procedure/operative reports. Please see Appendix 1 for all variables that will be extracted from charts. Any PHI that is collected as part of this prospective study will be maintained in the secure database.

Standard coagulation tests

Conventional coagulation tests (hemoglobin, platelet count, fibrinogen concentration, INR, aPTT, and PT) will be performed in both groups (ROTEM vs. conventional therapy) at two fixed time points (enrollment and within 3 hours after transfusion [which is also within 12 hours of procedure]) in order to compare both groups reliably. Transfusion of blood products (if indicated per the transfusion protocols) will occur within 24 hours of enrollment in both groups. In the post-procedure setting, tests will be performed if any bleeding occurs per the treating physician's discretion.

ROTEM

ROTEM will be performed according to the manufacturer's instruction, using equipment provided by Tem International GmbH. All tests will be performed at the bedside by a clinical perfusionist or study staff member trained to perform ROTEM. The point of care treatment will be guided with the Spine Surgery Algorithm based on the EXTEM, INTEM, FIBTEM and HEPTEM assays. ROTEM will be performed in both groups (ROTEM vs. conventional therapy) at two fixed time points (enrollment and within 3 hours after transfusion [which is also within 12 hours of procedure]) in order to compare both groups reliably.

The Ohio State University

WEXNER MEDICAL CENTER

F. Data Analysis

We will analyze blood product usage, peri- and post-procedure bleeding events, and hospital length of stay comparing ROTEM-guided transfusion protocol versus conventional, laboratory-based transfusion protocol. We will calculate any significant differences between these two cohorts using standard T-Test and multivariate analysis (ANOVA) with support from our Internal Medicine biostatistician.

All study patients will be continuously monitored by the study PI and sub-I's on the inpatient hepatology services. Safety monitoring will be performed on an ongoing basis throughout the entirety of the study. Based on our retrospective study using ROTEM in liver transplantation, we expect FFP transfusion rate to decrease by 50% and cryoprecipitate transfusion rate to increase in the ROTEM group with an overall decrease in blood product use. We expect bleeding rates to be similar in both groups.

IV. References

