Fibrinogen Pre transfusion	Fibrinogen (number)		
Fibrinogen Post transfusion	Fibrinogen (number)		
International Normalized Ratio (INR) Pre transfusion	International Normalized Ratio (INR) (number)		
International Normalized Ratio (INR) Post transfusion	International Normalized Ratio (INR) (number)		
Procedure performed	esophagogastroduodenoscopy = 1, colonoscopy = 2, neurosurgical procedures = 3, other endoscopy procedures = please type out procedure (e.g. endoscopic ultrasound)		
Blood product use prior to procedure	Number of Units		
Type of blood product given prior to procedure	Fresh Frozen Plasma (FFP) = 1, platelets = 2, cryoprecipitate = 3		
Packed Red Blood Cells (pRBC) use post-procedure	Number of units		
Total blood product use post-procedure	Number of units		
Significant blood loss peri-procedure	No = 0, Yes = 1		
Bleeding event 24 hours post-procedure	No = 0, Yes = 1		
Hospital Length of Stay	Number of Days		
Cost	Total cost of ROTEM reagents and supplies used and		
	lab tests (number)		

Division of Gastroenterolgoy, Hepatology & Nutrition Confidential

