COVER LETTER

Document date: 3/10/2020

Comparison of Blood Product Use and Bleeding Events During and After Endoscopic or Neurosurgical Procedures in Patients with Cirrhosis and Coagulopathy: Rotational Thromboelastometry Versus Conventional Therapy

NCT02457403

Statistical Analysis

Our sample size of thirty-four patients per group was based on a pilot project at OSUWMC that evaluated a total of sixteen patients. The same variables were studied in the pilot project, but no statistically significant results were found. We powered our study for the primary outcome of intra-operative blood loss based on the results of the pilot data.

Patient characteristics and laboratory values were compared between the two groups. Fisher exact tests were used to test for significant differences between the ROTEM and conventional coagulation groups with discrete variables such as race and gender. With continuous variables that were approximately normally distributed (BMI, MELD, and age), two-sample t-tests were used to test for significant differences between groups. Due to the non-normality of all laboratory values and ICU length of stay, nonparametric Wilcoxon rank-sum tests were used to test for significance.

Blood product usage and blood loss during OLT comparing ROTEM guided transfusion therapy versus conventional coagulation therapy were also analyzed. Due to the non-normality of the data, nonparametric Wilcoxon rank-sum tests were used to test for significant differences between the two groups in terms of the use of the 5 different blood products and blood loss. The sum of pRBCs, FFP, platelets, cryoprecipitate, and Cell Saver in units was used as an indicator of total blood product use. Results are expressed as medians and interquartile ranges. A two-tailed P value <0.05 was considered significant.

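### The bleeding aim is a non-inferiority question with a 5-point margin, but the plan tests only for significant differences and never compares the bleeding difference with the margin

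*Protocol*

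**What the plan says.** - **Hypothesis (Protocol III.B).** The ROTEM protocol "will significantly decrease blood product usage without any increase in procedural bleeding complications". No limit is placed on the bleeding half of this sentence.
- **Aim and margin (Protocol III.D).** The secondary aim is "demonstrating that the proportion of bleeding events in ROTEM patients is equivalent to or less than the proportion in non-ROTEM patients". The ROTEM proportion "will be considered to be equivalent to that of the non-ROTEM group if the proportion is no more than 5% larger". With 10% bleeding assumed in both arms, this "requires a sample size of 446 patients per group".
- **Status (Protocol III.D).** "The secondary aim is exploratory in nature for the purposes of this protocol", because only 202 patients are planned.
- **Analysis (Protocol III.F).** Bleeding events are listed among the outcomes. The method for all listed outcomes is: "We will calculate any significant differences between these two cohorts using standard T-Test and multivariate analysis (ANOVA".
- **SAP, Statistical Analysis.** "Fisher exact tests were used to test for significant differences between the ROTEM and conventional coagulation groups" for discrete variables, with race and gender as the examples. Wilcoxon tests cover product use and blood loss, and the significance rule is two-tailed 0.05. The SAP mentions no bleeding-event proportion, margin or confidence interval for a difference.

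**The concern.** A one-sided aim with a margin is answered by asking whether the data exclude an excess larger than that margin. A difference test asks whether the data exclude zero. In a small trial it will usually fail to do so, even when bleeding really is higher. III.D uses the margin for sizing and states it as a criterion, but neither analysis section takes it up.

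The safety half of the trial's message is at stake. III.B pairs lower product use with no increase in bleeding. Under III.F the only formal evidence for the second half would be a non-significant p-value, which at 101 per group is the likely result even when ROTEM adds the full 5 points. The error rate of such a conclusion is neither stated nor controlled.

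**Working it through.** **Inputs.** Protocol III.D gives 10% bleeding in both arms, a 5% margin, 446 per group for the bleeding aim and 101 per group planned. It states 80% power for the primary aim only; I assume the same for bleeding. No alpha or sidedness is given for the margin comparison, so I show one-sided 0.05 and 0.025.

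**1. Reproduce 446.** n per group = (z_α + z_0.80)² × 2 × 0.1 × 0.9 / 0.05²
- One-sided 0.05: (1.645 + 0.842)² × 0.18 / 0.0025 = 445.1, rounded up to **446**. This matches.
- One-sided 0.025: 565.1, rounded up to 566. No match.
- Relative margin (0.5 points), one-sided 0.05: 44,515. No match.
- Difference test of 10% vs 15%: 686 two-sided, 540 one-sided, 726 two-sided with continuity correction. No match.

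The figure is not an error. Of the calculations tried, only non-inferiority with an absolute 5-point margin at one-sided 0.05 and 80% power gives it.

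**2. Power against the margin at 101 per group, true rates 10% and 10%.** SE = √(2 × 0.09 / 101) = 0.0422, and power = Φ(0.05 / 0.0422 − z_α).
- One-sided 0.05: Φ(1.184 − 1.645) = **32%**
- One-sided 0.025: Φ(1.184 − 1.960) = **22%**

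Exact binomial enumeration with a Wald interval gives 33.5% and 22.5%. If both arms show 10%, the upper limit is 1.645 × 0.0422 = +6.9 points (90% interval) or 1.960 × 0.0422 = +8.3 points (95% interval). Both lie above +5.

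**3. What the planned difference test does at 101 per group.** Exact enumeration over all pairs of event counts, two-sided 0.05:

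| True rates, conventional vs ROTEM | t-test non-significant | Fisher non-significant |
|---|---|---|
| 10% vs 15% (at the margin) | 81% | 86% |
| 10% vs 20% (illustrative) | 48% | 55% |

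At 10% vs 15%, the rule that the upper 90% Wald limit must be below +5 points wrongly claims non-inferiority in **5.5%** of trials. At equal 10% rates, 64% of trials give a non-significant t-test while the 90% interval fails to exclude +5 points.

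**4. One possible result.** With 10/101 conventional and 19/101 ROTEM events, the difference is 9/101 = +8.9 points and the t-test p = 0.07. SE = √(0.099 × 0.901/101 + 0.188 × 0.812/101) = 0.0489, so the 90% interval is +0.9 to +17.0 points. The difference test is not significant, yet the estimate exceeds the margin and the interval excludes zero.

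**5. At the SAP's 34 per group.** The t-test is non-significant in 90% of trials at 10% vs 15%. Power against the margin at one-sided 0.05 is 17%.

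**The case against.** The strongest reply is that III.D already concedes the point: it gives 446 per group as the requirement, plans 202 in total and calls the aim exploratory. No confirmatory bleeding claim is planned, and the proposed analysis would probably not deliver one either. This stands as a limit on severity. But the label explains why the trial is too small, not why a difference test suits a margin question. III.B and III.F do not repeat it, and low power makes an interval more useful, because non-significance is then the expected result.

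A second reply is that the documents never say a non-significant test will be read as no increase, and that III.D already supplies a criterion. Both statements are accurate. However, III.D gives no test or confidence level for its criterion. Applied to the observed proportions alone, it would call ROTEM equivalent in 54% of trials when the true rates are 10% and 15%, so it does not rescue the plan.

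Third, the SAP describes blood loss during OLT in 34 patients per group, so its silence on bleeding events may reflect a wider mismatch with this trial. That is fair. It also means that the SAP cannot fill the gap.

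Finally, one-sided 0.05 and 80% power are inferred from a numerical match, and the only significance rule stated is two-sided 0.05, which would pair more naturally with a 95% interval. The sponsor must confirm the level; both versions are given here.

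**Conclusion.** The concern holds. The stated method does not address the stated bleeding aim, and neither document carries the margin into an analysis. At 101 per group, a true excess equal to the margin goes undetected by the planned t-test in 81% of trials, against a 5.5% wrong-claim rate for a 90% interval rule. Changing to Fisher's test would not help.

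The percentages depend on the protocol's assumed 10% base rate, which it extrapolates from bronchoscopy; they would shift with another rate. The 10% vs 20% case is illustrative and not taken from the documents. The figure of 446 is sound under the inferred settings. Because the aim is declared exploratory, this should be fixed but does not undermine the primary comparison.

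**What to change.** - **III.F:** replace the difference test for bleeding with wording such as: *Bleeding will be analysed as the risk difference (ROTEM minus conventional) with a two-sided 90% confidence interval. Non-inferiority will be claimed only if the upper limit is below +5 percentage points. A non-significant difference test will not be reported as no increase.*
- **III.D:** if the sponsor confirms it, state that 446 per group rests on one-sided 0.05 and 80% power, which matches the 90% interval. If a two-sided 95% interval is preferred, the matching figure is 566 per group, and 446 gives Φ(0.05/0.0201 − 1.960) = 70% power. Either way, state the power at 101 per group: 32% or 22%.
- **III.B:** mark the bleeding part of the hypothesis as exploratory.
- **SAP:** carry the same analysis over, with power restated if the number per group differs from 101.

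As a matter of detail, the new sentence should name the bleeding variable it uses, since Appendix 1 records both peri-procedure blood loss and "Bleeding event 24 hours post-procedure".

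The cost is wording only; enrolment stays at 202. The drawback is that the stated power is unfavourable and the trial will most likely be unable to claim non-inferiority on bleeding.

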Several studies utilizing ROTEM have shown that maximum clot firmness and fibrinogen levels are reliable predictors of perioperative bleeding complications and need for massive transfusions of blood products [3]. In patients undergoing liver transplantation, use of ROTEM guided hemostatic therapy correctly predicted hypofibrinogenemia, thrombocytopenia, and decreased clot firmness [4]. Furthermore, researchers suggest that while PT and INR are used as a prognostic indicator and to guide blood product management, that these tests are poor predictors of bleeding risk in liver disease [5]. This is an important realization, which challenges the current practice of correcting an abnormal INR with fresh frozen plasma prior to invasive procedures, even though INR cannot accurately predict bleeding risk, as it measures only one of the many components of coagulation and clot stability. Used in other scenarios where coagulopathy is encountered, studies have revealed the utility of ROTEM use in liver transplantation, significant hemorrhage, cardiac surgery, and detecting coagulation disorders in trauma [6].

WEXNER MEDICAL CENTER

Application of ROTEM hemostatic therapy and algorithm-guided blood products resuscitation before and during endoscopies may lead to more judicious use of blood products for cirrhotic patients with coagulopathy, as point of care testing will reveal information on the coagulation status of the patient to guide transfusions. In cardiac surgery patients who also had coagulopathy, point of care ROTEM testing resulted in lower cumulative blood product usage (including packed red blood cells, pooled platelets, and fresh frozen plasma), as well as lower post-operative mechanical ventilation time, length of intensive care unit stay, and six month mortality [7]. Cirrhosis-related coagulopathies represent an even more significant derangement in natural clotting and anticoagulation factors, and ROTEM may provide a more holistic approach to understanding where a particular patient lies on the spectrum from a high bleeding risk to a high clotting risk.

III. Procedures

A. Research Design

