Appendix 4: Schedule of Events

	Enrollment	< 3 hours after transfusion and < 12 hours of procedure	Peri-procedure	24 hours post- procedure
Consent	\checkmark			
Randomization	\checkmark			
ROTEM ¹	✓	✓		
Blood Collection ²	✓	✓		
Assess for Bleeding			\checkmark	✓
¹ Includes INTEM, EXTEM, HEPTEM, FIBTEM; ² Includes fibrinogen, PT/INR/aPTT, Hemoglobin;

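### Thrombosis and transfusion reactions are not defined, recorded or compared by arm, so the comparative safety reading rests on bleeding alone

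*Protocol*

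**What the plan says.** Protocol, II Background, presents ROTEM as a way to see where "a particular patient lies on the spectrum from a high bleeding risk to a high clotting risk". Clotting risk is therefore part of the trial's own rationale.

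Protocol, III.F Data Analysis, citing a retrospective study in liver transplantation, expects plasma (FFP) use to fall by half, the "cryoprecipitate transfusion rate to increase in the ROTEM group", and total product use to fall. The same paragraph says that the investigators will watch study patients continuously and that safety will be monitored throughout the study.

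Protocol, III.E, describes data capture: "Please see Appendix 1 for all variables that will be extracted from charts". The harm fields in Appendix 1 are "Significant blood loss peri-procedure" and "Bleeding event 24 hours post-procedure". Red-cell and total product use after the procedure are also listed. There is no field for thrombosis, transfusion reaction, any other adverse event, or death.

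Protocol, Appendix 4, has one clinical outcome row, "Assess for Bleeding", ticked peri-procedure and at 24 hours. The hypothesis (III.B), the secondary objectives (III.C) and the analysis list (III.F) name bleeding as the only harm. The SAP adds neither thrombosis nor transfusion reaction.

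**The concern.** The two arms are expected to differ in how much product is given and in which products are given. Bleeding is one possible consequence. Clotting, which the protocol itself raises, is another, and reactions to the transfused products are a third. A plan that records only the first can report only the first by arm.

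At stake is what may be said about safety at the end. If ROTEM lowers product use with similar bleeding, readers will ask whether thrombosis or transfusion reactions differed. The planned data set could not answer, whether the true difference favoured ROTEM, went against it, or was nil.

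**Working it through.** **1. Where each harm appears in the plan**

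| Place | Bleeding | Thrombosis | Transfusion reaction |
|---|---|---|---|
| Background (II) | yes | yes, as clotting risk | no |
| Hypothesis and objectives (III.B, III.C) | yes | no | no |
| Analysis list (III.F) | yes | no | no |
| Safety monitoring text (III.F) | no event named | no event named | no event named |
| Appendix 1 | two fields | no | no |
| Appendix 4 | one row | no | no |
| SAP | blood loss | no | no |

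Clotting risk enters the rationale and then drops out of everything that is measured or analysed.

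**2. The plan's own safety figure**

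III.D gives 446 per group for the bleeding aim, from 10% in both groups and a 5-point margin. It states neither alpha nor power for this aim. With one-sided 0.05 and 80% power:

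n = (1.645 + 0.842)² × (2 × 0.10 × 0.90) / 0.05² = 445.1, rounded up to 446.

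This reproduces the figure; one-sided 0.025 gives 566 and does not. So one-sided 0.05 and 80% power are inferred. With 101 per group, the standard error is √(0.18/101) = 0.0422, and power is Φ(0.05/0.0422 − 1.645) = Φ(−0.46), about 32%. With 34 per group it is about 17%. The one harm that is measured is thus itself underpowered, and III.D accordingly calls that aim exploratory.

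**3. What recording the events would give in a single arm**

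With zero events in n patients, the exact one-sided 95% upper bound p solves (1 − p)ⁿ = 0.05, so p = 1 − 0.05^(1/n).

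- n = 101 (protocol): 1 − 0.05^(1/101) = 2.9%. The upper limit of a two-sided 95% interval is 1 − 0.025^(1/101) = 3.6%.
- n = 34 (SAP): 1 − 0.05^(1/34) = 8.4%. The two-sided limit is 10.3%.

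These are best-case, single-arm bounds. They say nothing about the difference between arms.

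**4. What it would give between arms**

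The documents give no thrombosis or reaction rate, so the control rates below are assumptions. The test is two-sided at 0.05, the alternative is a doubling (p₂ = 2p₁), and there are n = 101 per arm:

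power = Φ[(p₂ − p₁ − 1.96 × SE₀) / SE₁],

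with SE₀ = √(2p̄(1 − p̄)/n), where p̄ is the mean of p₁ and p₂, and SE₁ = √((p₁(1 − p₁) + p₂(1 − p₂))/n).

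For 2% against 4%: SE₀ = 0.0240, SE₁ = 0.0240, and power = Φ[(0.02 − 1.96 × 0.0240)/0.0240] = Φ(−1.13), about 13%.

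| Assumed control rate | Power for a doubling, 101 per arm | Per arm for 80% power |
|---|---|---|
| 1% | 8% | 2319 |
| 2% | 13% | 1141 |
| 3% | 18% | 749 |
| 5% | 27% | 435 |

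The normal approximation is rough when only a few events are expected, but the conclusion does not depend on its precision. These outcomes can be described in this trial but not tested.

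**The case against.** Four arguments deserve weight.

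*Safety is monitored.* A reader might infer that thromboses would go unnoticed. The documents do not support that: III.F promises continuous monitoring, so an event could well be seen and treated. What stands is narrower. That text names no event, definition, time window, form or comparison by arm, so it protects the individual patient but supplies no comparative data.

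*The documents predict no extra clotting.* A reader might also infer from the cryoprecipitate sentence that ROTEM would raise thrombosis. The same sentence expects plasma to halve and total use to fall, the expectation comes from a different setting, and the Background offers ROTEM as a way to locate risk, not as a source of it. The direction is open. This removes any claim of harm but not the gap in measurement.

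*Reporting may exist elsewhere.* The completeness statement in III.E concerns chart-extracted variables. The contents of Appendices 2 and 3 and the consent pages are not in the text available here, so adverse-event reporting there cannot be excluded. This stands as a limit. It does not alter Appendix 1, Appendix 4, III.F or the SAP, which determine what is analysed.

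*The scope is deliberate and power is poor.* The hypothesis concerns procedural bleeding only, no sentence claims overall safety, and both transfusion protocols were already in use at the centre. This is fair, and it keeps the point at the level of an improvement. Low power is not a reason to omit counts, though: bleeding is kept as an exploratory outcome with 101 per group against a stated need of 446.

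**Conclusion.** The point holds as a gap in comparative safety data. The plan changes product mix by arm and cites clotting risk, yet it defines, records and compares only bleeding. It cannot show whether thrombosis or transfusion reactions differ between arms in either direction. It does not follow that ROTEM is unsafe, or that events would be missed at the bedside.

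The gain from closing the gap is modest: with zero events, an upper bound of 2.9% per arm at 101 or 8.4% at 34, and at most 27% power for a doubling over the assumed 1% to 5% range. The group size is itself unsettled, because the SAP gives 34 per group and describes blood loss during liver transplantation, while the protocol gives 101 per group for endoscopy and neurosurgery. Both sizes are shown for that reason.

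Label: cheap improvement. The primary comparison is unaffected.

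**What to change.** - **Appendix 1:** add two Yes/No fields, each with type and date, covering randomisation to discharge: clinically diagnosed venous or arterial thrombosis, and transfusion reaction of any type. Give each a short written definition.
- **Appendix 4:** add a row for these two outcomes and a discharge column. The present schedule ends at 24 hours post-procedure, so the existing bleeding row cannot carry them.
- **III.F and SAP:** report counts by arm, and the between-arm difference, with confidence intervals, beside bleeding. Label the table descriptive and plan no hypothesis test.

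Cost: two chart-extracted fields, one schedule row and column, and one table. Hospital stay is already an Appendix 1 variable, so charts must be followed to discharge anyway. No visit, test or screening imaging is added, and no transfusion rule changes. The remaining cost is abstraction time, which the documents do not allow to be quantified.

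Three limits should be stated with the table. Only clinically diagnosed in-hospital events are captured. Time at risk varies with length of stay, which is itself an outcome and may differ by arm, so length of stay should be shown alongside. Only the proceduralist is stated to be blinded, so care teams could look harder in one arm.
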